The study will consist of three (to a maximum of six) sequential cohorts of approximately 10 participants each. The cohorts will be dosed one after the other for a total of 30 (to a maximum of approximately 60) participants. This is an adaptive study and for a particular cohort, safety, incidence of infection and incidence of clinical illness will be evaluated on Day 14 to inform whether the ABO809 dose needs to be changed for dosing of the next cohort (see Section 6.5.1). If there are no safety issues, and the expected incidence of infection and illness are observed in one cohort, the next cohort will be dosed at the same dose level (see Section 6.5.1 for details). If the dose of ABO809 is changed from one cohort to the next, additional cohorts may be added to further evaluate Cryptosporidium infection and clinical illness following dosing with ABO809.

The study will consist of up to a 28-day Screening/Baseline period, an ABO809 administration and inpatient monitoring period, an outpatient follow-up period, and a study completion evaluation on Day 56. Additionally, Post-Study Follow-Up Calls will be conducted at 6 and 12 months after ABO809 administration. A CHIM diary will be provided to each participant to collect information on the participant's clinical symptoms.

Participants will receive a single oral dose of ABO809 on Day 1.

Cryptosporidium infection is defined as the presence of oocysts in at least 1 stool sample starting 72 hours following the administration of ABO809 (or sooner if associated with symptoms suggestive of diarrheal illness) and up to Day 10.

If clinical symptoms associated with cryptosporidiosis occur earlier than 72 hours post-administration, then stool samples after the onset of symptoms can be collected for parasitological evaluation for the primary endpoint. Normal bowel transit time varies from 30 to 40 hours, and therefore \geq 72 hours is chosen to minimize the chance of detecting only passively excreted oocysts given orally.

Resolution of *Cryptosporidium* infection is defined as no evidence of *Cryptosporidium* in stool samples collected over ≥ 2 consecutive days.

Stool samples will also be collected and sent to the laboratory in instances of relapse symptoms suggestive of *Cryptosporidium* infection until Day 28. Participants experiencing diarrheal symptoms between Day 28 and Day 56 may return for an unscheduled visit and provide stool for assessment of *Cryptosporidium* infection.

[figure not shown]

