	Commercially Confidential Informat	tion	
Occult Blood			
Cryptosporidium Antigen by EIA ^{10, 12}			

Period	Post-Study Follow-Up		
Visit Name	Post-Study Follow-Up Call		
Days	6 Month Phone Contact Commercially Confidential Information	12 Month Phone Contact on	
lgA			
	Commercially Confidential Informa	tion	
Evaluation of Clinical Signs and Symptoms ⁶			
CHIM Diary			
Standard of Care Drug Administration (Nitazoxanide) ⁸			
Concomitant medications			
Adverse Events	S ¹⁵	S ¹⁵	
•	Commercially Confidential Information	on	
Safety Follow-Up Call for Study Participants	S	s	
Study completion information			

Commercially Confidential Information

² Serum pregnancy tests at Screening and Day 28. Urine pregnancy test at Baseline.

³ Before ABO809 administration.

⁴ Participants should make every attempt to bring self-collected stool specimen to the clinic for each Outpatient Follow-Up visit. In the 24 hours prior to each Outpatient Follow-Up visit, all stools should be collected.

⁵ During screening, the first diarrheal stool, and the first diarrheal stool with relapse after clinical clearance will be tested for enteral pathogenic micro-organisms.

⁶ Includes number and frequency of diarrheal episodes, stool weight, volume, and grading (see Section 8.3.2, Section 8.4.1, and Appendix 1). Additionally, includes evaluation of nausea, vomiting, abdominal pain or discomfort, abdominal tenderness, abdominal rebound, abdominal distension, fecal urgency, diarrhea, flatulence, tenesmus, poor appetite, dehydration, fever, and electrolyte imbalance

⁸ Nitazoxanide to be administered per Prescribing Information (i.e. 500 mg every 12 hours for 3 days). Nitazoxanide administration will be captured on the standard concomitant medication page, and no specific CRF is required.

Page **50** of **81** Protocol No. CABO809A02101

Period	Post-Study Follow-Up	
Visit Name	Post-Study Follow-Up Call	
Days	6 Month Phone Contact	12 Month Phone Contact

¹¹ Additional tests can be done at the discretion of the Investigator e.g., in the case of dehydration.

Commercially Confidential Information

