Cryptosporidium infection: is defined as the presence of oocysts in at least 1 stool sample starting 72 hours following the administration of ABO809 (or sooner if associated with symptoms suggestive of diarrheal illness), up to Day 10 or Day 28 (separately). If clinical symptoms associated with cryptosporidiosis occur earlier than 72 hours post-administration, then stool samples after the onset of symptoms can be collected for parasitological evaluation. Oocysts will be detected by a commercially available diagnostic EIA test and confirmed by a DFA test if the EIA is positive. The tests will be performed at a Clinical Laboratory Improvement Amendments (CLIA) certified laboratory. Samples that test negative for Cryptosporidium by EIA will be reported as negative for Cryptosporidium without confirmation by DFA.

Resolution of *Cryptosporidium* **infection:** A *Cryptosporidium* infection will be considered resolved when no evidence of *Cryptosporidium* is detected in stool samples collected over ≥ 2 consecutive days. Please refer to the definition of "Number of days to resolution of Cryptosporidium infection" for further details.

Number of days to Cryptosporidium infection onset: is defined as the first occurrence of positive EIA test if it is at/after 72 hours post-challenge, otherwise as the first occurrence of positive EIA test with clinical diarrhea symptoms (if earlier than 72 hours), minus the date of dosing.

Number of days of Cryptosporidium infection: is defined as all days that have at least 1 positive EIA test.

Number of days to resolution of Cryptosporidium infection: is defined as:

- 48 hours after the last occurrence of positive EIA test during the inpatient period following the initial admission into the unit or,
- 48 hours after the last occurrence of positive EIA test during the inpatient period following the readmission into the unit or during the outpatient period up to Day 20 (without clinical diarrhea symptoms and before the start of NTZ) or,
- if there is a clinical relapse during the outpatient period, 48 hours after the last occurrence of positive EIA test with GP60 result showing recrudescence or,
- if clinical relapse during the outpatient period with GP60 result showing reinfection, 48 hours after the last occurrence of positive EIA test before onset of clinical symptoms,

i.e., the last positive EIA test date minus the dosing date +3.

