2.4 Analysis supporting primary objective(s) (PD analysis set)

2.4.1 Primary endpoint(s)

The primary endpoint is *Cryptosporidium* infection up to Day 10 (inclusive). This is defined as detection of oocysts

- in at least one fecal sample at \geq 72 hours after ABO809 administration
- or sooner than 72 hours if associated with symptoms suggestive of diarrheal illness, in at least one fecal sample after ABO809 administration.

Fecal stool samples will be assessed for *Cryptosporidium* infection using a commercially available diagnostic EIA test and confirmed by DFA test if the EIA is positive. Tests will be performed at a CLIA certified laboratory. Samples that test negative for *Cryptosporidium* by EIA will be reported as negative for *Cryptosporidium* without confirmation by DFA.

To overcome stool-to-stool and day-to-day oocyst shedding variability, up to 3 consecutive stool specimens, produced about 3-4 hours apart and on the same day will be tested. If at least one of the stool samples is *Cryptosporidium* positive, the participant will be considered infected. Otherwise, the participant will not be considered infected.

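### The infection timing variables in SAP 2.1.1.1 do not follow the SAP's own definitions of infection and resolution

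*SAP*

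**What the plan says.** SAP 2.1.1.1 defines infection first. It needs oocysts in at least one stool from 72 hours after dosing, or sooner if symptoms point to diarrheal illness. It also fixes the assay: "Oocysts will be detected by a commercially available diagnostic EIA test and confirmed by a DFA test if the EIA is positive". The primary endpoint in SAP 2.4.1 repeats both conditions, with the result "confirmed by DFA test if the EIA is positive". Protocol Section 3 explains the time limit, which "is chosen to minimize the chance of detecting only passively excreted oocysts given orally".

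The timing variables in the same SAP section read differently:

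- Days of infection "is defined as all days that have at least 1 positive EIA test".
- Onset "is defined as the first occurrence of positive EIA test if it is at/after 72 hours post-challenge". Otherwise it is the first positive EIA before 72 hours that comes with diarrhea symptoms. The dosing date is subtracted.
- Resolution is first defined in words, as stool free of Cryptosporidium over two or more days in a row, with a cross-reference to a day count. The day count places resolution 48 hours after the last positive EIA. Without relapse, it uses positives from the inpatient stay or "during the outpatient period up to Day 20 (without clinical diarrhea symptoms and before the start of NTZ". It is computed as "the last positive EIA test date minus the dosing date +3".

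SAP 2.5.2 shows time to onset and time to resolution as Kaplan-Meier curves. SAP 2.5.3 censors a participant who takes rescue medication, discontinues, dies or reaches the end of the study before the event. Outpatient visits fall on Days 14, 17, 21, 24 and 28, and footnote 4 to Protocol Table 8-1 says: "In the 24 hours prior to each Outpatient Follow-Up visit, all stools should be collected".

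**The concern.** Time to onset and resolution of infection is a separate secondary objective, and the model is meant to serve later trials of therapies and vaccines. Natural clearance time is a figure those trials would build on. A programmer who follows SAP 2.1.1.1 as written would meet four mismatches:

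1. Days of infection can include passive passage of the inoculum, which the 72-hour rule exists to exclude.
2. An EIA result that DFA did not confirm can set onset or resolution.
3. A participant who is still shedding can enter the Kaplan-Meier curve as resolved.
4. Onset and resolution are counted on scales one day apart.

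**Working it through.** The plan gives no figure of its own to reproduce here. The check applies the written rules to constructed participants. Dosing is Day 1 with no Day 0 (SAP 2.1.1), so Day d is d − 1 elapsed days, and 72 hours falls on Day 4.

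**Case A: passive shedding.** Symptom-free positives on Days 2 and 3, then confirmed positives on Days 6 to 9.
- Days of infection as written: 2 + 4 = 6. Counting only positives that meet the infection definition: 4.
- Onset: the first positive is not at or after 72 hours, so the main branch fails. The fallback branch needs symptoms, so it fails too, and a literal reading leaves onset undefined. The natural reading gives 6 − 1 = 5.

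**Case B: unconfirmed EIA.** EIA positive but not DFA confirmed on Days 4 and 14; confirmed positives on Days 7 to 10.

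| Variable | Any positive EIA | DFA-confirmed only |
|---|---|---|
| Onset | 4 − 1 = 3 | 7 − 1 = 6 |
| Days of infection | 6 | 4 |
| Resolution (formula with +3) | 14 − 1 + 3 = 16 | 10 − 1 + 3 = 12 |

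**Case C: persistent shedding.** Positive samples dated Days 6 to 10, 14, 17 and 21; no relapse; nitazoxanide started on Day 21.
- The window ends at Day 20, so the last counted positive is Day 17, and resolution is 17 − 1 + 3 = 19.
- The SAP does not say on which scale censoring times are counted. In elapsed days, as for onset, rescue is at 21 − 1 = 20. As 19 comes before 20, SAP 2.5.3 does not censor, and the participant is an event while still positive. On the study-day scale rescue is at 21, with the same outcome.
- The outcome depends on when rescue starts (elapsed days):

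| Nitazoxanide start | Elapsed days | Outcome against 19 |
|---|---|---|
| Day 18 | 17 | censored |
| Day 19 | 18 | censored |
| Day 20 | 19 | tie, counted as event by the usual convention |
| Day 21 | 20 | event |

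**Scale.** If the last positive is on Day 10, 48 hours later is Day 12, which is 11 elapsed days. The formula gives 10 − 1 + 3 = 12, which is the study-day number. Onset on Day 6 is given as 5, the elapsed time. The gap between the two is 12 − 5 = 7 days, when the calendar gap is 12 − 6 = 6.

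**Observability.** Outpatient visits are 3 or 4 days apart, with stool collected over the preceding 24 hours. That schedule can hardly show negative stools on two consecutive days after discharge, so the worded definition of resolution is difficult to apply there.

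**The case against.** The strongest reply is that the SAP's intent is clear and only its shorthand is loose.

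- **DFA.** SAP Table 1-1 states DFA confirmation in the shedding endpoint for this objective, and SAP 2.4.2 states it for the by-visit table. Confirmed positives are therefore the evident intent. This stands, but the derivation rules do not say so, although other parts of the SAP do.
- **Onset.** A reader might infer that onset uses any raw positive EIA. It does not, because the rule carries the 72-hour and symptom conditions. The faults there are the missing DFA condition and the literal gap in Case A.
- **Passive-only shedders.** The objective covers participants who developed an infection, so someone positive only on Days 2 and 3 falls outside it. The inflated day count also does not feed the Kaplan-Meier curves. Both points stand, but infected participants with earlier passive positives are still miscounted.
- **Resolution.** A reader might infer that the SAP never asks for a negative sample. Its worded definition does; only the formula omits it. This is an internal conflict.
- **Persistent shedders.** SAP 2.5.3 censors those who start rescue early enough, and SAP 2.3.4 allows nitazoxanide before Day 21. Stool brought to the Day 21 visit may also be dated Day 20, which gives 20 − 1 + 3 = 22, after rescue at 20, hence censored. Case C is therefore one route to error and does not describe every persistent shedder.
- **The +3.** It is a valid study-day number, and the diarrhea variables use it too. The offset is constant, but onset is not on the same scale.

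**Conclusion.** The point holds as a set of inconsistencies in secondary timing variables. Followed as written, the rules add 2 days to infection in Case A. In Case B they move onset by 3 days, days of infection by 2 and resolution by 4. In Case C they turn a censored time of 20 days into an event at 19. The +3 adds one day to every resolution time relative to onset. Case B assumes that positive EIA is read literally. Case C assumes a sample dated Day 21 and rescue starting that day. The primary endpoint keeps the 72-hour and DFA conditions and is not affected.

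The number of participants affected cannot be derived from the documents, and two estimates that a reader might attempt are not supported:

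- **False-positive EIAs.** Specificity is not given. Assuming 95%, 99% or 99.9%, and 21 independent, truly negative samples (3 a day on Days 4 to 10), the chance of at least one false positive is 1 − 0.95^21 = 66%, 1 − 0.99^21 = 19% or 1 − 0.999^21 = 2%. Protocol 8.3.1 allows up to 3 samples a day, so 21 is a maximum. Infected participants have fewer truly negative samples, and only false positives before onset or after clearance move those two dates.
- **Persistent shedding.** Protocol 4.1 cites excretion limited to 14 days in up to 86% of participants with diarrhea, and beyond 28 days in 5%. The first rate is for participants with diarrhea, and shedding past Day 14 is not the same as being positive on both Days 17 and 21.

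**What to change.** In SAP 2.1.1.1:

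1. Define a qualifying positive: EIA positive, DFA confirmed, and at or after 72 hours or earlier with symptoms. Use the first one for onset, the days with at least one for days of infection, and the last one for resolution.
2. Count resolution as a Kaplan-Meier event only when documented negative samples follow the last qualifying positive. In the unit this can be two consecutive negative days. After discharge it needs a rule the visits can support, for example two consecutive negative scheduled samples, reconciled with the protocol's two-consecutive-day definition. The rule should also cover a participant who leaves on Day 10 with only one negative day.
3. Include any Day 21 sample taken before nitazoxanide, and state whether samples carry the collection date or the visit date. If no qualifying negatives follow, right-censor at the last sample or the start of rescue.
4. Use +2 for 48 hours, so that onset and resolution share the elapsed-day scale. This must go together with item 2. Alone, it moves Case C to 17 − 1 + 2 = 18, which ties with a Day 19 rescue start that is now censored.

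The cost is SAP wording and programming on samples already scheduled. More participants will be censored, so median times will be less precise. SAP Section 4, which now declares no changes, should record the outpatient rule as a change from the protocol. An interval-censored analysis is optional.

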2.2 Analysis sets

For all analysis sets, participants will be analyzed according to the dose of ABO809 received (*C. parvum* oocysts, also referred to as "treatment").

The full analysis set (FAS) and safety analysis set (SAF) will be comprised of all participants who took one dose of ABO809 during the treatment period.

The Pharmacodynamic (PD) analysis set includes all participants with available parasitological and clinical data and with no protocol deviations with relevant impact on PD data. Fecal stool samples will also be assessed for other enteric pathogens which may cause diarrheal illness. Any participant with a positive test for these other enteric pathogens will be excluded.

The protocol deviation codes are summarised in Appendix Section 5.6.

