6.2.2 Prohibited medication

Except for protocol allowed concomitant medication or any medication which may be required to treat adverse events, no medication other than study treatment will be allowed from the date the participant signs the inform consent until EOS.

Participants should not receive any antiperistaltic, antidiarrheal agents or stool softeners from Screening through Day 28. These agents include, but are not limited to, bismuth subsalicylate, atropine and diphenoxylate, loperamide, octreotide, opium tincture, cholestyramine, colestipol, colace, or lactulose. Participants should not consume yogurt, kefir or probiotics (e.g. *Saccharomyces boulardii*) up to Day 21 or initiation of nitazoxanide, whichever comes first. All medications, procedures and significant non-drug therapies (including physical therapy and blood transfusions) administered after the participant is enrolled into the study must be recorded on the appropriate Case Report Forms.

In addition, other than those administered per protocol, participants should not receive any antibacterial or anti-parasitic therapy with possible activity against *Cryptosporidium* up to Day 28 (see Section 6.2.3).

Warfarin or drugs that prolong the QTc interval are not permitted between Screening and Day 28 unless deemed necessary by the Investigator (participants on warfarin or drugs that prolong the QTc interval are not permitted to enter the study (see Section 5.2).

Vaccinations are not permitted between Day -14 and Day 28 but are permitted outside this window (including COVID-19 vaccinations).

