A second course of nitazoxanide and/or other antiparasitic drug(s) (e.g. paromomycin alone or in combination with azithromycin) may be considered for participants with severe diarrhea or treatment failure after nitazoxanide monotherapy at the discretion of the Investigator. The duration of treatment will depend upon the participant's response to therapy. Although controlled, large-scale trials are lacking, the use of combination therapy is supported by findings from small case series (Smith et al 1998). Paromomycin (500 mg three times daily for one week) is generally used as an alternative agent if nitazoxanide cannot be used. All antimicrobial therapy for cryptosporidiosis administered before Day 28 will be recorded in eCRF as a concomitant medication.

Participants will not receive nitazoxanide if:

- they did not shed oocysts at any time after Day 3 and
- they did not have diarrhea between Day 1 and Day 21 and
- there was no diagnosis of cryptosporidiosis in any of the participant's household contacts between Day 11 and Day 21

In participants with severe diarrheal illness, oral and/or intravenous hydration, and replacement of electrolytes as needed, is expected as part of the standard of care management of adverse events (dehydration and severe diarrhea). Fluid replacement therapy will be recorded as a concomitant medication in the eCRF.

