12.1 Analysis sets

For all analysis sets, participants will be analyzed according to the dose of ABO809 (*C. parvum* oocysts, also referred to as "treatment").

The safety analysis set will include all participants that received ABO809.

The PD analysis set includes all participants with available safety, parasitological and clinical data and with no protocol deviations with relevant impact on PD data.

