5.1.3.3 Other imputations

N/A

5.2 **Prohibited medications**

Table 5-4 Table of prohibited medication with respective ATC codes

Prohibited medication	ATC code	ATC name
Antiperistaltic, antidiarrheal agents or	A02BX22	Bismuth subsalicylate
stool softeners	A03BA01	Atropine
	A07DA01	Diphenoxylate
	A07DA03	Loperamide
	H01CB02	Octreotide
	A07DA02	Opium tincture
	C10AC01	Cholestyramine
	C10AC02	Colestipol
	A06AA02	Docusate sodium
	A06AD11	Lactulose
Antithrombotic agents and other	B01AA03	Warfarin
agents prolonging QTc interval		
Antibacterial agents and other anti-parasitic therapies	A07AA06	Paromomycin alone or in combination with azithromycin
Yogurt, kefir, probiotics	N/A	N/A
vaccinations	N/A	N/A

AEs coding/grading 5.3

Grading will be assessed using the U.S. Food and Drug Administration's (FDA) "Toxicity Grading Scale for Healthy Adult and Adolescent Volunteers Enrolled in Preventive Vaccine Clinical Trials (2007)". For AE reporting based on laboratory values, local laboratory normal ranges may be used at the discretion of the Investigator, and if so, must be used consistently throughout the study. These may differ from the normal ranges given in the FDA grading scale. In case of such discrepancies, the Investigator will take into consideration the FDA recommendations as to the magnitude of deviations from normal provided in the FDA grading scale.

For AEs that are not contained in the "Toxicity Grading Scale for Healthy Adult and Adolescent Volunteers Enrolled in Preventive Vaccine Clinical Trials (2007)" the following categorization will be used:

- Mild: usually transient in nature and generally not interfering with normal activities
- Moderate: sufficiently discomforting to interfere with normal activities
- Severe: prevents normal activities

Stools will be graded according to this Stool Grading System by the Investigator. Grades 1 and 2 are considered normal stool and Grades 3-5 are considered diarrheal stool.

Table 5-5 Stool Grading System

Clinical Stool Classification	Stool Grade	Stool Description
Normal stool	1	Formed stool which does not take the shape of the container
Normal stool	2	Soft stool which does not easily take the shape of the container
Diarrheal stool	3	Thick liquid stool which does take the shape of the container
Diarrheal stool	4	Opaque watery stool
Diarrheal stool	5	Rice water stool, clear watery stool

Levine et al 1988, Sack et al 1998, Tribble et al 2009

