5.6 Rule of exclusion criteria of analysis sets

Table 5-6 Protocol deviations leading to exclusion

	9	
Analysis Set	Criteria that cause subjects to be excluded	
SAF	Not treated with study treatment;	
PD	Not having informed consent; Not treated with study medication;	
	Not meeting entry criteria;	
	No evaluable, parasitological and clinical data;	
	Use of prohibited medication or vaccination during the study;	

6 Reference

Clopper, C. J. and Pearson, E. S. (1934), "The Use of Confidence or Fiducial Limits Illustrated in the Case of the Binomial," *Biometrika*, 26, 404-413.

Collett, D. (1994), Modeling Survival Data in Medical Research, London: Chapman & Hall.

ICH E9(R1) Harmonized Guideline: addendum on estimands and sensitivity analysis in clinical trials to the guideline on statistical principles for clinical trials. Final version on 20 November 2019.

Toxicity Grading Scale for Healthy Adult and Adolescent Volunteers Enrolled in Preventive Vaccine Clinical Trials (2007). Guidance for Industry. U.S. Food and Drug Administration (Internet) Available from: (Accessed 09 July 2021).

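### The primary analysis set drops participants for a co-pathogen test that, after dosing, only participants with diarrhea can have, so set membership depends on a post-dose outcome

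*SAP*

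**What the plan says.** SAP 2.4 assigns the primary infection analysis to the PD analysis set. SAP 2.5 does the same for the incidence and characteristics of diarrheal illness and for time to onset and resolution of infection.

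SAP 2.2 builds that set from participants with parasitological and clinical data and no relevant deviation. It then adds a further rule: "Any participant with a positive test for these other enteric pathogens will be excluded". No sampling window is attached.

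Footnote 5 to Protocol Table 8-1 says when stools are tested: "During screening, the first diarrheal stool, and the first diarrheal stool with relapse after clinical clearance will be tested for enteral pathogenic micro-organisms".

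Protocol 12.1 has no such rule: "The PD analysis set includes all participants with available safety, parasitological and clinical data and with no protocol deviations with relevant impact on PD data". SAP Table 5-6, which lists the grounds for exclusion, does not contain it either, and SAP Section 4 declares no change to the protocol-specified analyses.

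SAP 2.2 also defines a full analysis set (FAS) of everyone dosed, but the readable efficacy sections do not use it. SAP 2.4.4 and 2.4.5 plan no sensitivity or supplementary analysis of the primary endpoint.

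A related wording problem sits in the SAP tables. Table 5-6 excludes from the PD set for "Use of prohibited medication or vaccination during the study", and Table 5-4 lists "Paromomycin alone or in combination with azithromycin" among prohibited agents without exception. Protocol 6.2.3 names the same agents as possible rescue treatment. On vaccination, Protocol 6.2.2 says: "Vaccinations are not permitted between Day -14 and Day 28 but are permitted outside this window".

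**The concern.** After dosing, a participant who never has a diarrheal stool is never tested for another pathogen and cannot be removed by this rule. A participant with diarrhea is tested and can be. Being in the primary analysis set thus depends on diarrhea, which underlies a secondary endpoint and is closely related to the primary one.

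The primary endpoint is specific to Cryptosporidium: an EIA-positive stool confirmed by DFA (SAP 2.4.1). A second pathogen does not undo that result. As worded, someone confirmed infected by Day 10 could still be deleted because of a finding in a relapse stool weeks later.

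The study exists to supply an infection rate and an illness rate for later trials in this model. Without an all-dosed result beside the PD-set result, a reader of the report could not see how far selection had moved either rate.

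**Working it through.** **Who can be removed, and when.** Current infectious diarrhea on screening tests is among the entry exclusions (Protocol 5.2, criterion 2), so the rule acts mainly after dosing. The trigger for testing is one stool of grade 3 to 5. Clinical diarrheal illness needs more: at least two diarrheal events within 24 hours on at least two days (SAP 2.1.1.1). Three kinds of participant can therefore be removed:

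- infected and ill;
- uninfected, with diarrhea from another cause;
- with some diarrhea, but never meeting the illness definition.

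**Reproducing the plan's own figures.** Protocol 12.8 assumes 90% infection and 70% clinical symptoms. Take the largest x with P(X ≥ x) ≥ 0.80, then the 1-sided 80% exact lower limit L(x, n) = the 0.20 quantile of Beta(x, n − x + 1).

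| n | Infection: x, P, L | Stated | Symptoms: x, P, L | Stated |
|---|---|---|---|---|
| 20 | 17, 0.867, 74.1% | 74% | 12, 0.887, 48.1% | 48% |
| 30 | 26, 0.825, 78.6% | 78% | 19, 0.841, 53.99% | 53% |
| 60 | 52, 0.858, 81.6% | 81% | 39, 0.838, 58.8% | 58% |

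All six match when truncated to whole percent. They allow for no exclusions.

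**Illustration: infected and ill participants removed.** Start from the expected counts at 30 dosed, 0.9 × 30 = 27 infected and 0.7 × 30 = 21 ill. The number removed, k, is an assumption, because the documents give no co-pathogen rate. The rates become (27 − k)/(30 − k) and (21 − k)/(30 − k). Lower limits are 1-sided 80% exact.

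| k | Infection (lower limit) | Illness (lower limit) |
|---|---|---|
| 0 | 27/30 = 90.0% (82.4%) | 21/30 = 70.0% (60.8%) |
| 1 | 26/29 = 89.7% (81.8%) | 20/29 = 69.0% (59.5%) |
| 2 | 25/28 = 89.3% (81.2%) | 19/28 = 67.9% (58.2%) |
| 3 | 24/27 = 88.9% (80.5%) | 18/27 = 66.7% (56.8%) |
| 4 | 23/26 = 88.5% (79.8%) | 17/26 = 65.4% (55.2%) |

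**The same in expectation.** If a fraction q of ill participants is removed, all of them infected, illness becomes 0.7(1 − q)/(1 − 0.7q) and infection (0.9 − 0.7q)/(1 − 0.7q). At q = 5%, 10%, 20% and 30%, illness is 68.9%, 67.7%, 65.1% and 62.0%. Infection is 89.6%, 89.2%, 88.4% and 87.3%.

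**Illustration: the opposite direction.**

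- One uninfected participant removed: infection 27/29 = 93.1%, up 3.1 points.
- One participant removed who had diarrhea but did not meet the illness definition: illness 21/29 = 72.4%, up 2.4 points.

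**The medication and vaccination wording.** Tables 5-4 and 5-6, read literally, would also exclude a participant given paromomycin as rescue or vaccinated after Day 28. Against that reading, Table 5-6 is headed as a list of protocol deviations. Protocol 6.2.2 exempts anti-parasitic treatment given per protocol, SAP 2.3.4 files paromomycin under rescue medication, and Protocol 6.2.2 allows vaccination outside its window. The passages conflict on their face, but the weight of the text is against exclusion.

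**The case against.** The rule has a rationale. The aim is to learn whether the challenge agent causes diarrhea, and counting illness in someone carrying another pathogen could inflate the model's attack rate. That stands for the illness endpoints, where either choice can be defended if both results are shown. It does not carry over to a Cryptosporidium-specific infection endpoint.

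Exclusions may be few. Participants are screened, domiciled with infection control until Day 10 and on a restricted diet. With one infected and ill exclusion in 30, infection moves by 0.3 points and illness by 1.0. This also stands, and it is why no co-pathogen rate is claimed here.

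The trial is single-arm and descriptive, with no success threshold in the readable primary analysis, and Protocol Section 12 leaves further analysis detail to the SAP. This lowers the severity. It does not explain why SAP Section 4 declares no change when the SAP adds an exclusion to the primary population.

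Four stronger readings are tempting, and the documents do not support them:

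- *Both rates are pulled down.* The direction depends on who is removed, as the two upward examples show.
- *Rescue with paromomycin, or vaccination after Day 28, removes participants.* This needs a literal reading of Tables 5-4 and 5-6 that Protocol 6.2.2 and SAP 2.3.4 contradict. Nitazoxanide is not in Table 5-4 at all.
- *The severest courses vanish from the report.* Adverse events, including cryptosporidiosis symptoms and events of special interest, are summarised in the safety set. The loss is confined to PD-set efficacy summaries.
- *The FAS is never used.* Parts of the SAP, including 2.5.6, are redacted or unreadable, so this can be said only of the readable efficacy sections.

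**Conclusion.** The concern holds as a should-fix. Membership of the primary analysis set depends on a post-dose test that is triggered by diarrhea, has no time limit and is not declared as a change from the protocol. No primary sensitivity analysis is planned that would show its effect.

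The size cannot be computed from the documents. Under the assumed one to four infected and ill exclusions in 30, infection falls by 0.3 to 1.5 points and illness by 1.0 to 4.6 points. A single exclusion of another kind can raise infection by 3.1 points or illness by 2.4.

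This rests on footnote 5 being the full testing schedule. The table row it belongs to is not readable, and SAP 2.2 gives no schedule of its own. A reader might also infer that dose choice is affected. That is not established, because Protocol 6.5.1 bases dose decisions on separately defined evaluable data, not on the PD set.

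**What to change.** - Analyse the infection endpoints in all dosed participants, using the FAS already defined, and keep co-pathogen-positive participants in.
- Report illness rates in the FAS and, as a sensitivity analysis for attribution, again with co-pathogen-positive participants excluded.
- Record the change of analysis population in SAP Section 4.
- Reconcile SAP Tables 5-4 and 5-6 with Protocol 6.2.2 and 6.2.3 and SAP 2.3.4, so that medication or vaccination the protocol permits is not read as a deviation leading to exclusion.

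The cost is SAP wording and one further run of the same tables. Some illness of mixed cause stays in the main illness rate, and the sensitivity run shows how much it matters. The FAS can also bring in a dosed participant with no stool result in the window. SAP 2.4.1 as worded would count that person as not infected, and the amended text should say so explicitly.
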